1.2 Disease Background

Over the past 7 years, data has emerged from numerous countries supporting the safety and efficacy of prostatic artery embolization (PAE) for the treatment of lower urinary tract symptoms (LUTS) in the setting of benign prostatic hyperplasia (BPH) (1). In response, the Food and Drug Administration (FDA) recently granted a de novo classification to Merit Medical Systems to expand the indications for Embosphere Microspheres to include PAE for the treatment of BPH. Moreover, it has given 510(k) clearances to both Embozene Microspheres and HydroPearl Microspheres.

Medication is the first line therapy for lower urinary tract symptoms (LUTS) secondary to BPH. These medications include alpha-adrenergic inhibitors, 5-alpha reductase inhibitors and phosphodiesterase inhibitors. While these medications are effective in improving urination in many men, there are also troubling side effects including retrograde ejaculation, erectile dysfunction, gynecomastia, lightheadedness, nasal congestion and loss of libido. Because of these side effects many men will discontinue the use of these medications.

It has been shown that PAE is very unlikely to result in a major complication and the minor complications tend to resolve without treatment within several weeks of the procedure. Therefore, because of its safety, and the untoward effects of BPH medications, it may be reasonable to suggest that PAE could be substituted as first line treatment for BPH. To further explore this notion, research comparing PAE to medication is needed.

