To address the secondary aim, we will tabulate the proportion of patients AEs pre- and post-PAE, comparing the proportion using McNemar's test. A p-value <0.05 for McNemar's test will be considered evidence that the proportion of AE's differs for medication, compared to PAE. A p-value >0.05 will be considered inconclusive. We will assume that the adverse events that occur following PAE will be attributed to the procedure and not medication.

We will present the percentage of prostate infarcted at 6 months and the incidence of minor complications at 1 month descriptively, and calculate 95% confidence intervals. Post-acquisition segmentation software will be used to measure infarct volume.

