9.4.2 Missing Value Documentation

The study case report form (CRF) is the primary data collection instrument for the study. All data requested on the CRF must be recorded. All missing data must be explained. If a space on the CRF is left blank because the procedure was not done or the question was not asked, write "N/D". If the item is not applicable to the individual case, write "N/A". All entries should be printed legibly in black ink. If any entry error has been made, to correct such an error, draw a single straight line through the incorrect entry and enter the correct data above it. All such changes must be initialed and dated. DO NOT ERASE OR WHITE OUT ERRORS. For clarification of illegible or uncertain entries, print the clarification above the item, then initial and date it.

Every attempt will be made to ensure that there is as little missing data as possible including reminder phone calls and follow-up phone calls, if a subject misses a

visit. If subjects withdraw, the reason for subject withdrawal will be documented in the study database.

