12.2 Adverse Event Questionnaires

Prostatic Artery Embolization Study

IRB#

PI:

Subject ID #: _____

Date of Visit: _____

Adverse Event

Have you experienced any of the following symptoms within the last month?

(Check all that apply)

- Nasal congestion
- Light headedness
- Retrograde ejaculation (Dry ejaculation)
- Priapism (Painful erection lasting 4 or more hours)
- Fatigue or weakness
- Headaches
- Hypotension (Low blood pressure)
- Heart fibrillation or Chest pain
- Swelling in hands, feet, or ankles
- Nausea
- Dizziness
- Fainting
- Erectile dysfunction
- Lower sex drive
- Gynecomastia (Male breast tissue)
- Dysuria (Burning with urination)
- Blood in Urine
- Blood in stool
- Blood in sperm
- Sores on penis
- Sores on buttocks

Form Completed By: _____

Signature

Date

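### The adverse-event tick list has no place for No, not asked or not applicable, and the plan does not say how an unticked item enters McNemar's test

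*Combined protocol and SAP*

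**What the plan says.** Section 12.2 holds the one adverse-event questionnaire shown in the documents. It asks "Have you experienced any of the following symptoms within the last month", adds the instruction "Check all that apply", and lists 21 symptoms. Several concern sexual function: retrograde ejaculation, erectile dysfunction, lower sex drive, blood in sperm. The form prints no No, None, not-asked or not-applicable option and does not ask about sexual activity.

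Section 9.4.2 sets a general rule for case report forms: "All missing data must be explained". N/D is to be written where a space is "left blank because the procedure was not done or the question was not asked". A separate code, N/A, is given for another case: "If the item is not applicable to the individual case".

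Section 8.3 addresses the secondary aim by tabulating adverse events before and after PAE and "comparing the proportion using McNemar's test", at the 0.05 level. It does not say whether the unit is any adverse event or each symptom, which version of the test is used, which post-PAE visit supplies the second half of the pair, or how an unticked item or a missing form is scored.

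The Time and Events Table (4.3) schedules adverse-event assessment at Visits 3 to 6 only.

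**The concern.** On a tick list, an empty box is the normal way of saying no. It is also what a skipped item looks like, and what a man leaves when the item cannot apply to him. Ejaculatory symptoms show this best: a man who did not ejaculate in the recall month has nothing to report, and the form cannot show that. These items matter to the trial's rationale. Section 1.2 motivates the study with six drug side effects, "retrograde ejaculation, erectile dysfunction, gynecomastia, lightheadedness, nasal congestion and loss of libido", and three of the six are sexual.

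McNemar's test uses only the pairs that change. If blanks were scored as no event, a man who ticked a symptom on medication and left it blank after PAE, for whatever reason, would become a discordant pair in favour of PAE. Blanks concentrated before PAE would work in the opposite direction. With 30 men, few such pairs are needed, and the ambiguity cannot be resolved from the data afterwards.

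**Working it through.** The plan states no power or expected count for this comparison, so there is no figure of its own to reproduce. (The 81.2% power in 8.2 belongs to the primary IPSS test and has no bearing here.)

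**Inputs from the documents.** 30 subjects; 20% dropout (8.2), so 30 × 0.8 = 24 complete pairs; level 0.05 (8.3), taken as two-sided because the test looks for a difference.

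**Step 1: how many one-way pairs reach p < 0.05?** Let b be the pairs with an event before PAE only and c the pairs with an event after PAE only. With k versus 0 pairs, the exact two-sided p is 2 × 0.5^k. The uncorrected chi-square is (b − c)²/(b + c) on 1 df, which equals k when c = 0.

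| b versus c | Exact | Chi-square, uncorrected | Chi-square, continuity-corrected |
|---|---|---|---|
| 4 vs 0 | 0.125 | 0.046 | 0.134 |
| 5 vs 0 | 0.0625 | 0.025 | 0.074 |
| 6 vs 0 | 0.031 | 0.014 | 0.041 |
| 7 vs 1 | 0.070 | 0.034 | 0.077 |
| 8 vs 1 | 0.039 | 0.020 | 0.046 |

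The exact test needs 6 versus 0, or 8 versus 1 if one pair goes the other way. The uncorrected chi-square needs 4 versus 0, or 7 versus 1. These thresholds depend only on the discordant pairs, so they are the same for 24 pairs as for 30.

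**Step 2: does blank-as-no raise the false-positive rate?** The documents give no prevalence, discordance or blank rate, so all three are assumptions. Let π be the true prevalence in both periods (no real difference), δ = 10% the true discordance, and m the share of true yes answers left blank after PAE only. Then

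- P(b) = (π − δ/2) × m + δ/2
- P(c) = (δ/2) × (1 − m)

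For π = 50% and m = 20%: P(b) = 0.45 × 0.20 + 0.05 = 0.14 and P(c) = 0.05 × 0.80 = 0.04. Summing the trinomial probabilities of all (b, c) with p < 0.05 gives the rejection rate:

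| Blanks | Test, pairs | π = 30% | π = 50% | π = 70% |
|---|---|---|---|---|
| None | Exact, 30 | 0.002 | 0.002 | 0.002 |
| 20% in both periods | Exact, 30 | 0.008 | 0.015 | 0.020 |
| 20% in both periods | Uncorrected chi-square, 30 | 0.048 | 0.047 | 0.043 |
| 20% after PAE only | Exact, 30 | 0.028 | 0.098 | 0.213 |
| 20% after PAE only | Uncorrected chi-square, 30 | 0.124 | 0.240 | 0.370 |
| 20% after PAE only | Exact, 24 | 0.013 | 0.052 | 0.128 |
| 30% after PAE only | Exact, 30 | 0.074 | 0.253 | 0.482 |

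**Step 3: what drives it?** Equal blank rates kept the rejection rate below 0.05 in each of these scenarios. One-sided blanks raised it, above 0.05 in many of them. A man who is sexually inactive in both periods is a no/no pair and contributes nothing to the statistic. The mechanism therefore needs blanks, or inactivity, that differ between periods.

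**The case against.** A reader might infer that the plan counts missing answers and sexually inactive men as free of the event, and that this alone would give a significant result. The documents do not support that. No section says how a blank is scored, and Step 3 shows that only a difference between periods matters. Nothing in the documents says that blanks will be more frequent after PAE than before.

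Other points also stand:

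- If the unit is any adverse event, a blank changes a man's status only when nothing else is ticked. Each of the six men would have to leave all 21 items blank after PAE. Section 5.4 cites rectal pain and/or dysuria in 9.1% and haematuria in 4.4%, so pairs in the other direction are plausible, at least early; 1.2 expects minor complications to resolve within several weeks.
- Telephone or teleconference contact is allowed only at Day 1 and Week 1 (4.1.8, 4.1.9). Subjects return in person at 3 and 6 months, and the adverse-event outcome in 2.3.2 is at 3 months. The form carries a visit date and a signature, so a form never worked through can be recognised.
- Adverse events are also recorded on case report forms (7.2) and in a log, with assessment by a licensed investigator (9.3.2). At least 25% of source documents are verified (9.4.1). No section says that the tick list alone feeds McNemar's test.
- N/D or N/A can be handwritten beside an item. It would be too strong to say that the form cannot comply with 9.4.2.
- One might also argue that 2.3.2 uses the wrong denominator for sexual items. It lists overall incidence, not item-level rates.

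What remains is narrower. The form offers no item-level place for these codes, the plan does not say how 9.4.2 applies to it, and 8.3 has no scoring rule. Signatures, log entries and source verification do not show whether a particular empty box was a considered no.

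**Conclusion.** The point holds as a minor gap in data collection and analysis specification. The form does not separate no from not asked or not applicable, and 8.3 leaves the scoring open. If blanks are read as no event and are more common in one period, 6 one-way pairs (exact) or 4 (uncorrected chi-square) could produce significance in either direction. The rejection rates in Step 2 rest on assumed prevalences, discordance and blank rates; they show what is possible, not what is expected. The documents do not establish that the comparison is biased towards PAE, or that sexual inactivity as such distorts it.

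Differential completeness is a practical possibility because no adverse-event assessment is scheduled at Visit 1 or 2: the documents do not show how the pre-PAE half of each pair is to be collected. The severity is minor because a secondary aim is affected.

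**What to change.** 1. In 12.2, replace the tick list with a response for each symptom: Yes, No, Not applicable (N/A), Not asked (N/D). State that the rule of 9.4.2 applies to this form.
2. Use the same form before and after PAE, and add the pre-PAE administration to the table in 4.3.
3. In 8.3, state that N/D or missing items are not scored as no adverse event, and report their number by period. State separately how N/A is handled. Name the unit (any event or per symptom), the post-PAE visit and the version of McNemar's test. If the unit is any event, say how a man with no Yes but some N/D or N/A items is classified.
4. Optionally, add a line on sexual activity in the last month to help interpret the ejaculation and erection items. A comparison restricted to men active in both periods should be no more than a labelled sensitivity analysis: it conditions on a post-treatment state and could drop men who are inactive because of erectile dysfunction.

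The cost is a one-page form change, one row entry in 4.3 and a few sentences in 8.3. The form takes slightly longer to complete, and there may be fewer complete pairs. The change has to come before data collection, because analysis cannot recover the distinction later.
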